### 9.4. M8 (Thiocyanate) Toxicity Analysis

To evaluate the impact of brensocatib treatment on AEs that might have potential association with M8 (thiocyanate), including hypothyroidism, hypotension, and neurotoxicity, additional investigations will be made.

The thiocyanate-related AEs will be identified using a hierarchical approach such that MedDRA FDA Medical Queries (FMQs) will be used when available and MedDRA Standardized Medical Queries (SMQs) will be used when an FMQ is unavailable. When an FMQ and SMQ are both unavailable, a Customized Medical Query (CMQ) will be created.

The following thiocyanate-related AEs will be identified.

- FMQs:
  - Hypotension (FMQ grouping: hypotension)
  - Seizures (FMQ grouping: Seizure)
  - Confusion (FMQ grouping: Confusional State)
- SMQs:
  - hypothyroidism (SMQ narrow category: hypothyroidism)
  - delirium (SMQ narrow category: noninfectious encephalopathy/delirium)
- CMO:
  - Hallucinations
    - (Preferred Terms):
      - Hallucination aggravated
      - Kinesthetic hallucination
      - Organic hallucinosis syndrome
      - Hallucinations
      - Hallucination NOS
      - Sensory hallucinations
      - Drug-induced hallucinosis
      - Hallucinating
      - Stump hallucination

For hypotension, blood pressure will also be investigated for abnormalities defined as:

- Systolic blood pressure <90 mmhg and diastolic blood pressure <60 mmhg, or
- Change from Baseline in systolic and diastolic blood pressure >=30 mmHg,

The number and percentage of participants with an AEs that might have potential association with M8will be presented in an overview table. The M8 concentrations in plasma, when

CONFIDENTIAL Page 77 of 139

available, will be described descriptively and changes from baseline until the time point the AE reported the very first time.

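### The Hallucinations query in SAP 9.4 is a closed nine-term list with no visual or auditory form; unless it is checked against MedDRA before lock, the hallucination count in the M8 overview can be too low

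*SAP*

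**What the plan says.** SAP 9.4 looks for adverse events that might be linked to M8 (thiocyanate): hypothyroidism, hypotension and neurotoxicity. Queries are chosen in a fixed order, with an FDA Medical Query (FMQ) first and a Standardized MedDRA Query (SMQ) second. Failing both, "When an FMQ and SMQ are both unavailable, a Customized Medical Query (CMQ) will be created".

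Six queries follow. Three are FMQs (hypotension, seizures, confusion) and two are narrow SMQs (hypothyroidism, delirium). The sixth, Hallucinations, is the only customized one, so it is the only query there whose content the sponsor wrote itself. Under the label "Preferred Terms" it has nine entries:

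- two narrow forms, "Kinesthetic hallucination" and "Stump hallucination";
- one entry that refers to the senses in general, "Sensory hallucinations";
- three wordings of the general concept: the plain plural, "Hallucination NOS" and the participle;
- three entries for aggravated, organic and drug-induced forms.

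Nothing in the wording opens the list to further terms. Appendix K, which holds other code lists for this SAP, has none for hallucinations.

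SAP 9.2 codes adverse events to primary system organ class (SOC) and PT in the latest MedDRA version. SAP 9.4 reports participants with M8-associated events in an overview table, and SAP 9.6 repeats the M8 analysis in adolescents.

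**The concern.** FMQs and SMQs are maintained outside the trial. A customized query captures only what its author lists. This list includes narrow forms of hallucination but names neither sight nor hearing, and it spends three of its nine entries on one concept. On its face it reads as a list that may not have been reconciled with the dictionary used for coding.

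A programmer who follows the SAP literally will match PT-coded events to these nine strings and leave out a hallucination event coded to any other PT. Hallucination is one of the neurotoxicity events that SAP 9.4 sets out to count. What is at stake is the accuracy of that count in the M8 overview and in the adolescent output.

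**Working it through.** The SAP gives no figure on this point, so there is none to reproduce. The check is textual, followed by one line of arithmetic.

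**Step 1. Content of the list.** Entries: 9. Entries containing the word visual: 0. Entries containing the word auditory: 0. The bare singular noun is not an entry either. Wordings of the general concept: 3. Counting those three as one leaves 9 − 3 + 1 = 7 distinct wordings.

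**Step 2. Matching level.** The list is labelled as PTs (SAP 9.4) and events are coded to PT (SAP 9.2). There are two ways to apply it:

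- *Literally.* An entry that is not a PT matches nothing, and an event coded to an unlisted PT is not counted.
- *After mapping.* Any entry that is not a PT is first replaced by its PT. The general concept is then probably captured. A modality-specific PT is captured only if one of the entries maps to it.

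The documents do not say which was intended. On either reading, what the query captures depends on the dictionary, which the documents do not contain.

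**Step 3. Effect on the count.** Let N be the participants in an arm with a hallucination event, m the number of those whose events are all coded outside the list, and n the arm size. The query reports (N − m)/n instead of N/n, so the shortfall is m/n. It is zero only if m = 0. Neither N nor m can be obtained from the documents, so the shortfall cannot be computed.

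**Step 4. Weight of one missed participant.** Planned sizes come from SAP 3.3: 540 adults per arm, and 16, 16 and 8 adolescents.

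| Output | Planned n | Points per missed participant |
|---|---|---|
| Brensocatib arm, all ages | 540 + 16 = 556 | 100/556 = 0.18 |
| Placebo, all ages | 540 + 8 = 548 | 100/548 = 0.18 |
| Brensocatib arm, adolescents | 16 | 100/16 = 6.25 |
| Placebo, adolescents | 8 | 100/8 = 12.5 |

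These are unit weights, not an estimate of how many participants would be missed.

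**Step 5. Where a missed event would still appear.** SAP 9.2 plans treatment-emergent events by SOC and PT (all, severe, serious, related, fatal, leading to withdrawal) and by PT alone. An event outside the list appears there under its own PT, not grouped with other hallucination events.

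**The case against.** The strongest reply is that absent words are not missed events. An undercount needs two facts: that visual and auditory hallucinations have their own PTs, and that none of the nine entries covers them. The documents show neither. "Sensory hallucinations" could on its face include sight and hearing. This stands, and it is why the point is conditional.

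A reader might infer that the list does omit visual and auditory events, or that the M8 count will be too low. The documents do not support that without the dictionary. A reader might also take the repeated general wordings as evidence of omission. They are not, since redundancy cannot lower a count. The same holds for the two word orders of one term in the Appendix K COPD list, which belongs to a different query. At most, repetition is a reason to check.

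The Confusional State FMQ or the delirium SMQ may also catch some of these events. That is possible, but their contents are not in the documents. SAP 9.4 does not say whether the overview has one line per query or a single total. In a single total, a participant counted under another query is not lost. With one line per query, the hallucination line would still be short.

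Finally, a reader might fear that a safety signal would be hidden. The tables in step 5 answer most of that, and SAP 9.6 also plans adverse event analyses in adolescents. What remains is that the grouped count, which is the purpose of SAP 9.4, could be incomplete.

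**Conclusion.** The point holds in conditional form and is of low importance. The Hallucinations query is a closed list at PT level, names no visual or auditory form, and gives the general concept in three wordings that are unlikely all to be distinct PTs. If hallucination events are coded to PTs outside the list, the count in the M8 overview and its adolescent repeat would be too low.

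That condition is an assumption which only the MedDRA version in use can settle, and the size of any shortfall cannot be computed from the documents. The output is descriptive, with no test or decision rule attached. Efficacy, the adverse events of special interest and the general adverse event tables are unaffected.

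**What to change.** Before database lock, and blinded:

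1. Check the nine entries against the MedDRA version used for coding.
2. Replace any entry that is not a PT with its PT.
3. Add the general hallucination PT and all modality-specific ones, including visual and auditory, where not already covered.
4. State the MedDRA version beside the list.

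The cost is one list edit in SAP 9.4 and a short blinded check by the existing medical team. No new data are needed, because events are already coded to PT. Timing matters: SAP Section 1 treats analyses not described in the plan and run after unblinding as post hoc, and a list changed then would be chosen with results in view. If the check shows that the nine entries already cover everything, little has been spent.

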## 6.4.3. Baseline Definition, Change from Baseline

According to Table 5 of the CSP ("Schedule of Assessments and Procedures"), the second visit (V2) is defined as "Baseline". However, the definition of the "Baseline" which is used to

CONFIDENTIAL Page 32 of 139

derive any changes of assessments during study conduct, e.g., laboratory parameters, depends on the timing of the first IP administration and can therefore be different from Baseline/Day 1/Visit 2. Therefore, unless otherwise stated, for the purpose of analysis baseline value is the last non-missing value prior to or at the date of the first dose of IP, considering also unscheduled visits. For participants who do not receive IP during the study, baseline is defined as the latest, non-missing collected value on or before Study Day 1.

Change from baseline will only be calculated for measures that have post-baseline records. Change from baseline is calculated as:

visit value – baseline value.

If either the baseline or visit value is missing, the change from baseline will be set to missing as well.

For summaries, whenever baseline is presented, the above baseline definition is used. That is, the baseline summary presented is in general not the summary of the (CSP defined) Baseline/Day 1 visit. Screening values will be listed but not summarized. Throughout the document, Baseline (capital B) refers to the visit Baseline/Day 1; baseline (lower case b) refers to the values derived using the baseline definition above.

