#### **Maximum reduction**

The lowest post-treatment change from baseline result will identify the maximum reduction for the respective participant.

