### 9.9. Vital Signs and Pulse Oximetry

Systolic and diastolic blood pressure, heart rate, respiratory rate, oxygen saturation, temperature, height, weight, and BMI will be collected at protocol specified visits.

Descriptive summaries of actual values and changes from baseline will be based on available data and will be provided by visit and treatment group.

Arithmetic mean plots of vital signs and oximetry parameters over time will be prepared. The standard deviation will be included at each sampled time point.

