### 9.10. Electrocardiogram

ECG parameters will be collected at protocol specific visits.

Descriptive summaries of actual values and changes from baseline will be based on available data and will be provided by visit. Investigator and central reading interpretation will be summarized by visit, too.

A categorical summary of QTcF interval will be provided using counts and percentages at baseline and maximum post-baseline by treatment for the following categories:

- Result >450 and  $\leq 480$  msec;
- Result >480 and <500 msec;
- Result >500 msec;
- Change from Baseline >30 and ≤60 msec;
- Change from Baseline >60 msec.

Safety 12-lead ECG data will be provided in a data listing.

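### SAP 9.4: the change limb of the hypotension blood-pressure definition, read with SAP 6.4.3, counts rises of 30 mmHg or more and cannot be met by a fall.

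*SAP*

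**What the plan says.** SAP 9.4 looks for adverse events that might be linked to the metabolite M8, hypotension among them. Hypotension events are found through an FDA medical query, "Hypotension (FMQ grouping: hypotension". A check on measured values is added: "For hypotension, blood pressure will also be investigated for abnormalities defined as" two conditions. The first is "Systolic blood pressure <90 mmhg and diastolic blood pressure <60 mmhg, or". The second is "Change from Baseline in systolic and diastolic blood pressure >=30 mmHg". Section 9.4 does not mark the second condition as a decrease, put a minus sign on it, call it a magnitude, or give its own formula for change.

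The formula is in SAP 6.4.3, where change from baseline is "visit value – baseline value". Other parts of the SAP follow the same sign convention. Under SAP 6.8, "The lowest post-treatment change from baseline result will identify the maximum reduction for the respective participant", so a reduction is a low, negative change. SAP 9.10 uses "Change from Baseline >60 msec" for QTcF, where a rise is the concern.

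For vital signs in general, SAP 9.9 plans this: "Descriptive summaries of actual values and changes from baseline will be based on available data and will be provided by visit and treatment group".

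**The concern.** A rule meant to find low blood pressure should be met by falls. The job of the second limb is to add participants whose pressure dropped a long way without reaching the low levels in the first limb. Under the SAP's own formula it cannot do that. It picks up people whose pressure went up and labels them as having a hypotension abnormality.

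At stake is a participant-level safety flag on a question that the sponsor chose to pre-specify. SAP 9.6 repeats the M8 analysis in adolescents, so the same rule carries over to that subgroup. The SAP introduction also classes any analysis not described there and run after unblinding as post hoc, so a corrected flag added late would carry that label.

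**Working it through.** **Inputs**

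- Limb 1 (SAP 9.4): systolic < 90 and diastolic < 60 mmHg.
- Limb 2 (SAP 9.4): change >= 30 mmHg in systolic and diastolic pressure.
- Change (SAP 6.4.3): visit minus baseline.
- The plan states no count or rate for this check, so there is no figure to reproduce. All blood-pressure readings below are illustrative.

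**Sign.** If pressure falls by D > 0, change = -D, and -D >= 30 is impossible. Limb 2 therefore needs a rise of at least 30 mmHg: in both pressures if both must qualify, or in at least one if either is enough.

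**Worked cases**

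| Baseline | Visit | Change | Limb 1 | Limb 2 as written | Limb 2 as a decrease (<= -30 in both) |
|---|---|---|---|---|---|
| 150/95 | 112/62 | -38/-33 | no | no | yes |
| 100/60 | 135/92 | +35/+32 | no | yes | no |

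The large fall is missed by the whole definition, and the rise is flagged.

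**Grid check.** Baseline and visit readings were run in 5 mmHg steps (baseline systolic 80 to 200 and diastolic 40 to 120; visit systolic 60 to 220 and diastolic 30 to 140; diastolic always below systolic), requiring both pressures to qualify. Of 150,540 combinations with a fall in systolic or diastolic pressure, 0 met limb 2. The 30,516 combinations that met it were all rises of at least 30 mmHg in both pressures. For equal falls of 30 to 79 mmHg, none met limb 2 under either the both or the either reading.

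**Which falls are lost.** Take an equal fall of D >= 30 in both pressures. Limb 1 flags it only if

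- baseline systolic - D < 90, that is, baseline systolic < 90 + D, and
- baseline diastolic - D < 60, that is, baseline diastolic < 60 + D.

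If baseline systolic >= 90 + D or baseline diastolic >= 60 + D, neither limb flags it.

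| D | Missed if baseline systolic is at least | or baseline diastolic is at least |
|---|---|---|
| 30 | 90 + 30 = 120 | 60 + 30 = 90 |
| 40 | 90 + 40 = 130 | 60 + 40 = 100 |

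Boundary check for D = 30:

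- 119/89 to 89/59 meets limb 1.
- 120/80 to 90/50 meets neither limb, since 90 is not below 90.
- 119/90 to 89/60 meets neither limb, since 60 is not below 60.

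**Alternative reading.** If limb 2 is taken as a magnitude (30 mmHg in either direction), falls are caught, but the rise from 100/60 to 135/92 is still flagged. Only a signed decrease matches the hypotension heading.

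**The case against.** The strongest reply is that the context supplies the direction. The line is introduced as a check for hypotension and stands next to a low-value limb, so a decrease is very probably meant, and a programmer may well code it that way. SAP 9.4 has no program code showing otherwise. It can be added that the safety section is not uniform about sign: Table 10 uses an absolute change for hemoglobin, and 9.3 gives a pocket-depth change with no direction.

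The second reply is that little information is lost. The opening of SAP 9 promises listings to accompany summaries, and protocol 10.4.7 and 10.4.7.3 plan subject-level listings of safety data and vital signs. The fall from 150/95 to 112/62 would be visible there. Section 9.4 also specifies no table, comparison or decision rule for the blood-pressure flags.

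The third is that both limbs use the same conjunction for systolic and diastolic, so it is inconsistent to call it open in the second limb only.

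What stands: the intent is fairly clear, the raw values are planned to be listed, and the both/either point is minor. None of this corrects the rule. The heading shows that the text conflicts with its purpose. The only formula in the documents that governs the line is signed, and a magnitude reading would still count rises. The hemoglobin entry says that its change is absolute; the blood-pressure line does not. Listings let a reader look for falls one by one, but they do not produce the pre-specified flag.

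**Conclusion.** The point holds with high confidence, and the line should be corrected. Followed as written, the second limb selects rises, adds no participant with a fall in both pressures, and misses large falls that do not reach both low thresholds.

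The consequence is limited. This is one limb of a descriptive check. The first limb still catches falls to its levels. The adverse-event query covers hypotension where an event was reported, and the SAP 9.9 summaries show changes with the correct sign, though by visit and treatment group and not by participant. Section 9.4 does not say that the flags enter the adverse-event count. No primary or secondary efficacy result is affected.

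The conclusion rests on the 6.4.3 formula applying to 9.4; neither document gives blood pressure a different sign. The baseline limits shown assume equal systolic and diastolic falls. How many participants would be misclassified cannot be stated without a blood-pressure distribution.

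**What to change.** Reconcile SAP 9.4 with 6.4.3 by writing the second limb as a decrease from baseline, that is, change <= -30 mmHg, keeping the sponsor's 30 mmHg figure. In the same line, state whether systolic and diastolic pressure must both meet it or whether either is enough. This takes no view on whether 30 mmHg is the right threshold. The cost is one SAP line and the matching program condition, with no new data. It should be done before unblinding so that the flag remains pre-specified.

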#### 9.5. Deaths

A listing of all AEs resulting in death will be provided.

### 9.6. Subgroup Analyses

Subgroup analyses for adverse events including AESI and M8 metabolite analysis will be reported in the adolescent subgroup (12-<18 years of age).

### 9.7. Clinical Laboratory Evaluations

Numeric laboratory parameters (hematology, chemistry, and urinalysis) will be summarized using descriptive statistics at baseline and at each post-baseline timepoint. Changes from baseline will also be summarized. Descriptive statistics at baseline and change from baseline is limited to continuous data. Categorical data, e.g., urinalysis, will be tabulated as well. A separate by-participant listing will be provided for abnormal values reported.

Shift tables from baseline to the worst result post-baseline including unscheduled assessments will be provided to assess changes in laboratory values. Worst values are results which have the highest distance to the normal range. Reference ranges established by the central laboratory will be used to determine shifts.

Participants experiencing ALT or AST  $\geq$  3 × upper limit of normal (ULN) and total bilirubin > 2 × ULN or ALT or AST  $\geq$  5 × ULN at any point during the study irrespective of an increase in ALP will be tabulated by treatment group. The elevations do not have to occur at the same time or within a specified time frame. Potential cases will be summarized descriptively and listed. In addition, individual (worst) ratio of ULN post-baseline will be presented graphically.

Arithmetic mean plots of laboratory values over time will be prepared for continues laboratory test. The standard deviation will be included at each sampled time point.

A summary of counts of participants with at least one abnormal laboratory value at any visit including unscheduled will also be provided.

Testing for HBcAb, HBsAb, HBsAg, HIV, and HCV will be conducted at Screening only. Those test results will be summarized and listed.

The number and percentage of participants with potentially clinically significant abnormalities (PCSA) will be summarized as defined in Table 10. For the determination of PCSA unscheduled assessment will be considered.

CONFIDENTIAL Page 78 of 139

Table 10: Criteria for Potentially Clinically Significant Abnormalities (PCSA)\*

Parameter		
code	Parameter	PCSA
Clinical Che	mistry	
SODIUM	Sodium (mmol/L)	<120.0 mmol/L
		>155.0 mmol/L
K	Potassium (mmol/L)	<3.0 mmol/L
		>6.0 mmol/L
MG	Magnesium (mmol/L)	<0.4 mmol/L
		>1.23 mmol/L
CA	Calcium (mmol/L)	<1.75 mmol/L
		>3.1 mmol/L
GLUC	Glucose (mmol/L)	<2.2 mmol/L
AST	Aspartate	> (5.0 x ULN) if baseline was normal or $>$ (5.0 x
	Aminotransferase (U/L)	baseline) if baseline was abnormal
ALT	Alanine	> (5.0 x ULN) if baseline was normal or $>$ (5.0 x
	Aminotransferase (U/L)	baseline) if baseline was abnormal
ALP	Alkaline Phosphatase	> (5.0 x ULN) if baseline was normal or $>$ (5.0 x
	(U/L)	baseline) if baseline was abnormal
BILI	Bilirubin, Total	> (3.0 x ULN) if baseline was normal or $>$ (3.0 x
	(umol/L)	baseline) if baseline was abnormal
LDH	Lactate Dehydrogenase	> (1.0 x ULN)
	(U/L)	
CREAT	Creatinine (umol/L)	> (3.0 x ULN) if baseline was normal or $>$ (3.0 x
CDE LEGIS		baseline) if baseline was abnormal
CREATCLR	Creatinine Clearance	<29.0 ml/min/1.73 m^2
TT ( )	(mL/min/1.73m2)	
Hematology	11. (7)	.00.0 //
HGB	Hemoglobin (g/L)	<80.0 g/L
WDC	T 1 (1000/T)	Absolute change from baseline >40.0 g/L
WBC	Leukocytes (10^9/L)	<2.0 10^9/L
NEUT	Neutrophils (10^9/L)	<1.0 10^9/L
LYM	Lymphocytes (10^9/L)	<0.5 10^9/L
DLAT	Distalate (1000/L)	>4.0 10^9/L
PLAT Uringlysis	Platelets (10^9/L)	<50.0 10^9/L
Urinalysis UGLUC	Chaosa Urina (ma/di)	Present
UPROT	Glucose, Urine (mg/dL)	
UPKUI	Protein, Urine (mg/dL)	<0.0 mg/dL >14.0 mg/dL
		~14.0 Hig/aL

CONFIDENTIAL Page 79 of 139

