#### 4.2.2.1. Reasons for Withdrawal/Early Discontinuation

A subject may decide to withdraw from the study at any time, for any reason, without prejudice to subsequent care or treatment by the Investigator. When this occurs, the subject should complete all the procedures for the Week 52 (EOT) Visit. Subjects who discontinue the treatment due to AEs should remain under observation until the resolution or stabilization of the AEs. A subject may be discontinued from the study drug treatment before completion for any of the following reasons:

- 1. Subject death
- 2. Subject experiences an AE(s)/SAE(s) that warrants discontinuation, as judged by the Investigator and/or Insmed Medical Director
- 3. A major protocol deviation, which, in the opinion/discretion of the Investigator and/or Insmed, compromises the data integrity of the study
- 4. Subject is noncompliant with the study drug treatment (defined as <80% compliance after at least 2 reeducation efforts)
- 5. Withdrawal by subject
- 6. Termination of the study by the Sponsor
- 7. Investigator discretion
- 8. Subject lost to follow-up
- 9. Subject pregnancy
- 10. Periodontal criteria met (see Section 9.10.3.2)
- 11. Skin criteria met (see Section 9.10.3.1)
- 12. Diagnosis of a malignancy during study, excluding carcinoma in situ of the cervix, or squamous or basal cell carcinoma of the skin
- 13. Serious infection, defined as any infection other than associated with a pulmonary exacerbation that:
  - a. Requires parenteral treatment with an antibiotic requiring admission to the hospital, or parenteral treatment with an antifungal, antiviral, antiparasitic, or antiprotozoal agent
  - b. Is opportunistic, such as TB or other infections whose nature or course may suggest an immunocompromised status
- 14. Subjects who develop neutropenia defined as ANC <1000/mm^3
- 15. Subjects who have the following:
  - a. ALT and/or AST values >3 × ULN and total bilirubin >2 × ULN, excluding confirmed Gilbert's Syndrome
  - b. Confirmed AST and/or ALT >5 × ULN (for more than 2 weeks).

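### The single worst-value rule for laboratory shift tables (SAP 9.7) drops a low neutrophil count when the same participant had a larger high one, so falls between 1.0 × 10^9/L and the lower limit are under-counted

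*SAP*

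**What the plan says.** SAP 9.7 states the purpose of the tables: "Shift tables from baseline to the worst result post-baseline including unscheduled assessments will be provided to assess changes in laboratory values". The selection rule follows: "Worst values are results which have the highest distance to the normal range". The limits come from the laboratory: "Reference ranges established by the central laboratory will be used to determine shifts". Their numerical values appear in neither document.

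The same section plans other outputs that bear on low counts:

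- "The number and percentage of participants with potentially clinically significant abnormalities (PCSA) will be summarized as defined in Table 10". In Table 10 the neutrophil criterion is low-only, below 1.0 × 10^9/L. The section adds: "For the determination of PCSA unscheduled assessment will be considered".
- "A separate by-participant listing will be provided for abnormal values reported".
- "A summary of counts of participants with at least one abnormal laboratory value at any visit including unscheduled will also be provided". No direction is stated for this count.
- Descriptive statistics and changes from baseline by visit.

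Protocol 4.2.2.1 gives, among the reasons for stopping study drug, "Subjects who develop neutropenia defined as ANC" below 1000/mm³. Protocol 10.4.8 also places the absolute neutrophil count in the pharmacodynamic analyses. SAP 6.8 limits pharmacodynamic parameters to NE, CatG and PR3, and SAP 13 does not record that the neutrophil count was dropped from them.

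**The concern.** A shift table exists to show how many participants moved out of range, and in which direction. With one value per participant chosen by distance alone, anyone who went out of range on both sides is counted on one side only. For counts that can rise several-fold, the side that wins will often be the high one.

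Neutrophils are where this matters most. The drug acts on enzymes activated during neutrophil maturation, and the protocol monitors for low counts. A dose-related tendency to mild or moderate falls would be expected to appear first as shifts to low, before anyone crosses 1.0 × 10^9/L. If some of those shifts are recorded as shifts to high, the table is weakest in the direction it most needs to show. Because the SAP no longer carries the pharmacodynamic view of the neutrophil count, the laboratory tables bear more of the weight.

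**Working it through.** The plan states no figure to reproduce, so the check is of the rule itself.

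**1. When is a low value displaced?** Let L be the participant's lowest value and H the highest, with LLN and ULN the reference limits.

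- Absolute distance: L is displaced when H − ULN > LLN − L, that is, H > ULN + LLN − L. Dividing both distances by the width of the range changes nothing. Since L cannot be below zero, the low-side distance never exceeds LLN, while the high side has no bound.
- Fold distance: L is displaced when H/ULN > LLN/L, that is, H > ULN × LLN / L. The bound on the low side no longer applies, but one direction is still dropped.

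The SAP does not say which scale applies.

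**2. Numbers.** The reference ranges below are assumptions (× 10^9/L). Each entry is the high count above which the low count disappears from the shift table.

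| Assumed range | L = 1.2, absolute | L = 1.2, fold | L = 0.9, absolute | L = 0.9, fold | L = 0, absolute |
|---|---|---|---|---|---|
| 1.5–7.0 | 7.3 | 8.75 | 7.6 | 11.7 | 8.5 |
| 1.8–7.7 | 8.3 | 11.6 | 8.6 | 15.4 | 9.5 |
| 2.0–7.5 | 8.3 | 12.5 | 8.6 | 16.7 | 9.5 |
| 2.0–8.0 | 8.8 | 13.3 | 9.1 | 17.8 | 10.0 |

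Example for 2.0–7.5 and L = 1.2: absolute 7.5 + 2.0 − 1.2 = 8.3; fold 7.5 × 2.0 / 1.2 = 12.5.

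**3. What the other outputs recover.** The protocol threshold of 1000/mm³ equals 1000 × 10^6 per litre, or 1.0 × 10^9/L, which is the Table 10 limit. A count of 0.9 is therefore tabulated whatever the participant's highest value was. A count of 1.2 is not. It appears in the by-participant listing, adds to the undirected count of any abnormal value, and contributes to the by-visit statistics. The minimum in those statistics is one number per arm and visit, not a number of participants. None of these gives a by-arm, low-direction incidence for counts from 1.0 up to LLN.

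**4. Illustrative size.** These figures come from a log-normal model in which every input is assumed: 6 or 7 post-baseline visits (Protocol Table 5 schedules six draws, at Weeks 4, 16, 28, 40, 52 and 56), geometric mean 4 to 5, between-subject SD 0.35 on the log scale, and a doubled count at one visit in 15% of participants. The outcome is the share of participants with a value below LLN who would not be shown as low.

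- 70% fall at one visit, within-subject SD 0.30 to 0.35, ranges from 1.5–7.0 to 2.0–8.0: 13–38% on absolute distance, 6–22% on fold distance.
- The same fall with geometric mean 4, SD 0.20, range 1.8–7.5, absolute distance: about 10%.
- 50% fall, geometric mean 4, SD 0.30, range 1.8–7.5, absolute distance: about 8%.
- No induced fall, SD 0.30, range 1.8–7.5, absolute distance: about 2.5–4%.

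Greater visit-to-visit variability raises each figure.

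**The case against.** The strongest reply is that the harm is already covered. The low count that matters under the protocol is below 1000/mm³, and Table 10 counts every such participant, with unscheduled assessments, in a criterion that no high value can displace. Neutropenia reported as an adverse event, or leading to withdrawal of study drug, is tabulated by system organ class and preferred term. All abnormal values are listed. This stands. A reader might infer that the plan hides neutropenia; the documents do not support that.

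Second, absolute distance is only one reading of the rule. Step 2 shows that the thresholds depend strongly on the scale. Even on absolute distance not every high excursion wins: with an assumed range of 2.0–7.5, a count of 8.0 (0.5 above) does not displace 1.2 (0.8 below). This also stands, but it leaves the point in place: the scale is undefined, and on either scale one direction is dropped.

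Third, the illustrative percentages reflect chosen inputs. The documents give no neutrophil reference range or variance, nothing in them suggests a 70% fall, and laboratory draws follow fixed visits rather than exacerbations. So a reader should not infer that a fifth or a third of low counts would go missing in this trial.

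Fourth, not every two-sided parameter is affected alike. Potassium is a weak example, since Table 10 already has both a low and a high criterion for it.

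None of this supplies the missing count for the band from 1.0 × 10^9/L to the lower limit.

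**Conclusion.** The point holds in limited form. As written, the rule gives a misleading shift table for participants who go out of range on both sides; this is a consequence of the stated rule, not a missing detail. The loss is confined to the by-arm incidence of falls below the lower limit that stay at or above 1.0 × 10^9/L, in participants who also had a larger high value. Participants whose only excursions were low are still shown correctly.

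The size cannot be derived from the documents. The illustrations run from a few per cent to more than a third of participants with a low value, depending on the reference range, distance scale, variability and size of fall assumed. They show that the loss need not be trivial, and they predict nothing about this trial. No efficacy analysis, error rate or adverse-event-of-special-interest analysis is touched. The change is still worth making before database lock, because the affected direction is the one of interest for this drug.

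**What to change.** In SAP 9.7, replace the single worst-value rule with two shifts for two-sided parameters: baseline to the lowest post-baseline value and baseline to the highest, both including unscheduled assessments. Do this at minimum for neutrophils, leukocytes and the other two-sided hematology counts. Keep one-directional tables where only one direction matters. If a single worst value is kept for any two-sided parameter, state the distance scale.

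The cost is a sentence or two in the SAP and a few extra table shells. It uses data already collected.
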